8.11 Biological specimen collection and testing

All samples will be obtained from study participants by trained study staff according to approved standard operating procedures. All samples will be processed according to the assay manufacturers' specifications. Some specimens collected from patients in this protocol will be analyzed immediately per standard antenatal care guidelines. Others will be transported, processed, and temporarily housed at the University Teaching Hospital (Lusaka, Zambia) and the UNC Project Malawi (Lilongwe, Malawi). Use of stored specimens for testing that is not specifically designated in this protocol will require additional regulatory approval. All laboratory testing will be performed by trained staff using standard operating procedures and according to specific assay manufacturers' specifications.

8.12 Quality control and quality assurance procedures

Standard Operating Procedures (SOPs) following manufacturer's protocols and detailing technical procedures involved (e.g. sample collection, processing and storage, assay procedures and how to interpret test results) will

be developed and used by the study team. Tests will only be performed by certified laboratory personnel. Site coordinators will complete annual recertification. The certification process is an opportunity to ensure the highest specimen quality and standardize collection techniques.

8.13. Data Management and Storage

Data collected from each participant will include sociodemographic information, relevant HIV and obstetrical history, and results of HIV testing. Study data management (e.g., data transmission, query resolution, etc.) will follow site data management standard operating procedures. Study identification numbers will be used on all forms and communications related to the study. A separate confidential register will link study identification numbers and participant names. All data instruments and registers will be securely stored. Data will be entered into a custom-built database and, where possible, will be validated via double entry. Computers and tablets will be encrypted and password protected and their access restricted to authorized study personnel. Backups of the data will be made on a weekly basis. Data may be transmitted electronically to the study investigators through secure cloud-based servers. Study information will not be released without written permission of the participant, except when necessary for monitoring by the relevant ethical committees or their designees. Data will be disposed of after completion of the study per country guidelines. At that time, electronic records, including linkage codes and identifiers, will be deleted. Paper records will be shredded prior to disposal.

8.14 Sample Size

The two parallel randomized trials in this protocol are each designed as pilot studies, so that we may obtain the necessarily preliminary data about outcomes and implementation to inform future, larger studies. As such, the sample sizes are based on feasibility considerations. Despite this general approach, we provide estimated power and precision of each trial for large differences between the intervention and control arms.

8.14.1 Sample size for Trial 1

We will enroll **100 HIV-positive pregnant women** in **Trial 1**, randomized 1:1 between the intervention and control arms ($n=50$ each), with randomization balanced (stratified) by site. The primary endpoint for Trial 1 is the proportion of participants retained and in care with viral suppression at 6-month follow-up. This composite outcome is calculated based on the entire randomized sample, with the approximately 10% of women lost to follow-up included in the denominator.

Figure 4 presents anticipated statistical power for the Trial 1 primary analysis over a range of scenarios. Control arm probabilities of the primary outcome (retained in care with viral suppression <40 copies/mL) are shown ranging from 0.70 to 0.85.[ref] Effect sizes (risk differences) are shown ranging from 0.10 to 0.25. Assuming $\alpha=0.05$ and the probability of being retained and in care with viral suppression in the control arm is 0.75, we anticipate approximately 82% power to detect an increase in viral suppression probability of 0.20 in the intervention arm (i.e., 75% vs. 95% retained with viral suppression in the control and intervention arms, respectively). For lower control arm probabilities of being retained in care with viral suppression (e.g., 0.70) there will be $\geq 80\%$ statistical power to detect a risk difference of 0.22 or larger. Power calculations were based on a two-sided likelihood ratio chi-square test for two proportions.

[figure not shown]

Figure 4: Statistical power in Trial 1 by effect size and control arm probability of retained in care with viral suppression (VS) at 6 months

The anticipated statistical precision for the Trial 1 and Trial 2 comparisons are presented in Table 4. For control and intervention probabilities of being retained and in care with viral suppression of 0.75 and 0.95, respectively, the anticipated 95% CI for the risk difference has length 0.263. This trial will provide preliminary data on the effectiveness of the intervention which can be leveraged in planning a larger, future trial.

Table 4: Anticipated statistical power and precision for Trial 1 and Trial 2

Population	N enrolled per arm	Assumed true probability of outcome*		Power [†]	Example results in expectation n tested / n evaluable (%)			
		Control	Intervention		Intervention	Control	Difference in probabilities (95% CI)	CI Width
Trial 1	50	75%	85%	24%	43/50 (86%)	38/50 (76%)	10 (-5.4, 25.4%)	30.8%
			90%	52%	45/50 (90%)	38/50 (76%)	14 (-0.6, 28.6%)	29.2%
			95%	83%	48/50 (96%)	38/50 (76%)	20 (6.8, 33.2%)	26.3%
Trial 2	100	30%	45%	59%	45/100 (45%)	30/100 (30%)	15 (1.7, 28.3%)	26.6%
			50%	83%	50/100 (50%)	30/100 (30%)	20 (6.6, 33.4%)	26.7%
			55%	95%	55/100 (55%)	30/100 (30%)	25 (11.7, 38.3%)	26.6%

* For Trial 1 (HIV-positive women), the outcome is retained and in care with viral suppression at 6 months. For Trial 2 (HIV-negative women), the outcome is retained and in care on PrEP at 6 months

† Using a likelihood ratio Chi-square test for two proportions, alpha=0.05

8.14.2 Sample size for Trial 2

We will enroll 200 HIV-negative pregnant women in Trial 2, randomized 1:1 between the intervention and control arms (n=100 each), balanced (stratified) by site. The primary endpoint for Trial 2 is the proportion of participants retained and in care with functional PrEP use at 6 months. This composite outcome is calculated based on the entire randomized sample, with the anticipated 10% of women lost to follow-up included in the denominator.

Figure 5 presents the anticipated statistical power for the Trial 2 primary analysis for a range of scenarios. The control arm probabilities of retained and in care with functional PrEP adherence at six months are shown ranging from 0.20 to 0.35; and effect sizes (risk differences) are shown ranging from 0.15 to 0.35. Trial 2 is powered to detect large increases in being retained in care with functional PrEP adherence between study arms. Assuming the probability of being retained in care with functional PrEP adherence in the control arm is 0.30, we anticipate approximately 82% power to detect an increase in the probability of functional PrEP adherence of 0.20 in the intervention arm (i.e., 30% vs. 50% in the control and intervention arms, respectively). For lower control arm probabilities of being retained in care with

[figure not shown]

Figure 5: Statistical power in Trial 2 by effect size and control arm probability of retained in care with pharmacologically measured functional PrEP at 6 months

functional PrEP adherence (e.g., 0.20) there will be $\geq 80\%$ statistical power to detect a risk difference of 0.18 or larger. Power calculations were based on a two-sided likelihood ratio chi-square test for two proportions and alpha=0.05. The anticipated statistical precision for the Trial 2 comparisons are presented in Table 4. For control and intervention probabilities of being retained and in care with functional PrEP of 0.30 and 0.50, respectively, the anticipated 95% CI has length 0.267. Like Trial 1, the primary objective of Trial 2 is to obtain preliminary data regarding the efficacy of the intervention which can support future trials.

8.15 Data Analysis Plan

8.15.1 General Approach

The two randomized pilot trials will be conducted in parallel for HIV-positive (Trial 1) and HIV-negative (Trial 2) pregnant women. All primary and secondary endpoints will be evaluated separately for each trial. In order to evaluate effectiveness, analyses will be conducted using an intention-to-treat approach, with women analyzed according to the arm they were randomly assigned. Appropriate descriptive statistics will be used throughout, n (%) for categorical data and median (25th, 75th percentile), mean (SD) and min-max for continuous measures.

Given the pilot nature of these studies, emphasis will be put on estimation and precision of measured effects, rather than null hypothesis testing. An alpha=0.05 will be used throughout to compute 95% confidence intervals (CIs), with no adjustment for multiplicity. In the case of small cell counts or analyses of continuous data with $n < 30$, 95% CI coverage properties of large-sample methods will be evaluated in simulation studies or existing exact statistical methods (e.g., exact CI for a risk difference) will be used. Given potential for precision loss with exact CI methods and the pilot nature of these studies, we will use large-sample methods (e.g., Wald CIs) when the nominal CI coverage level is tenable.

Missing (unevaluable) data are anticipated to be uncommon ($\leq 10\%$). The primary analyses are based on a composite endpoint of being retained in care with either viral suppression (Trial 1) or functional PrEP use (Trial 2), and thus complete case analyses will be conducted (i.e., missing viral load data = excluded). Women who are not retained in care will be counted in the denominator for the primary analysis. Sensitivity analyses will exclude women who were not retained in care.

8.15.2 Primary endpoint analysis of Trial 1 (ART adherence)

We will assess ART adherence by evaluating the viral suppression status of each study participant 6 months after study enrollment. Participants not lost to follow-up will be classified as either virally suppressed (< 40 copies/mL) or not virally suppressed (≥ 40 copies/mL). Women who are not retained for 6-month follow-up will be counted as failures and will contribute to the analysis denominator. The proportion of women who are retained and in care with viral suppression will be compared between randomization arms based on a linear-binomial model. To control for any site-specific effects, site (country) will be included as a covariate in the model. From the linear-binomial model, the site-adjusted risk difference of being retained and in care with viral suppression for the intervention arm versus the control arm will be calculated, along with a corresponding 95% CI. Results will also be described separately by country (Malawi and Zambia).

8.15.3 Primary endpoint analysis of Trial 2 (PrEP adherence)

We will assess PrEP adherence via drug concentrations of plasma tenofovir (TFV) and intracellular tenofovir diphosphate (TFVdp). Using published algorithms,⁷⁷ results from the plasma and upper layer of packed cells (ULPC) assays will be combined to develop a composite adherence score. The scale ranges from 0 to 5 and each category represents a distinct adherence pattern (Table 5). Our primary outcome for this analysis will be *functional* adherence, which we define as 4-5 or more doses per week (scores of 4 or 5). In sensitivity analysis, we will also consider a rigorous outcome of *optimal* adherence (score of 5, representing consistent daily dosing). Future published improvements upon this algorithm will be taken into consideration for sensitivity analyses prior to the final analysis.

Table 5: Adherence composite scores based on TFV and TVFdp concentrations, with doses estimated per interval ⁷⁷

Score	TFV in plasma	TVFdp in ULPc	Estimates doses per interval
0	None detectable	<10,000 fmol/mL	Low number or no doses in the interval
1	Detectable	<10,000 fmol/mL	A few doses in the entire interval
2	Any level	10,000 to 100,000 fmol/mL	1-2 doses per week
3	<10 ng/mL	>100,000 fmol/mL	Several doses early in the interval, followed by a stop in the 1-2 weeks leading up to sampling visit
4	>10 ng/mL	100,000 to 1,000,000 fmol/mL	4-5 doses per week
5	>10 ng/mL	>1,000,000 fmol/mL	Approximately daily dosing

In our primary analysis, we will compare the proportion of the sample retained in care with functional PrEP adherence at 6-month follow-up between the two randomization arms using a linear-binomial model. As with Trial 1, site (country) will be included as a covariate in the model. Women who are not retained for 6-month follow-up will be counted as failures and will contribute to the analysis denominator. From the linear-binomial model, the site-adjusted risk difference of being retained and in care with functional PrEP for the intervention arm versus the control arm will be calculated, along with a corresponding 95% CI. Results will also be described separately by country (Malawi and Zambia).

In addition to the primary analysis, assessing functional PrEP adherence as binary outcome, secondary analyses will compare the adherence composite scores between the study arms using a Wilcoxon rank-sum test. This analysis will be restricted to women with an evaluable adherence composite score.

8.15.4 Secondary endpoints analyses of Trial 1 and Trial 2

For both trials, incidence of social harms and other adverse events will be estimated by study arm, and individual events will be described using listings. Retention in the study will be described using frequency tables, and reasons for study drop-out will be tabulated. Participant deaths will be recorded along with the contributing cause(s) of death.

Adherence to ART and PrEP will be measured both by self-report and pharmacy measures. A medication possession ratio (MPR) will be estimated within study arm, and the difference in means between study arms will be compared using a 95% CI. An MPR of 80% or greater will be categorized as good adherence; this threshold will be used for additional analyses of a dichotomized endpoint (retained in care with MPR \geq 80% at 6-month follow-up). Analyzed risk difference will be estimated using the same approach as in the primary endpoints described above. Data visualizations will display individual-level data points and box-plots of adherence measures (e.g., MPR, pill counts). Self-reported adherence responses will be described within study arm. In Trial 2, incidence of maternal HIV infection will be estimated with a corresponding exact Poisson 95% CI. Additionally, detailed statistical analysis plans will be finalized prior to analysis of each trial.

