7.0 HYPOTHESES

The implementation of a multi-component adherence support strategy will increase retention in care with viral suppression among HIV-positive pregnant women on ART.

The implementation of a multi-component adherence support strategy will increase retention in care with functional PrEP adherence among HIV-negative pregnant women.

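### The Trial 2 score test and the retained-only sensitivity analyses compare women selected after randomisation; the likely effect is modest, but they should be labelled as descriptive and an all-randomised, site-stratified score comparison added

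*Combined protocol and SAP*

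**What the plan says.** Section 8.15.3 combines plasma and intracellular tenofovir results into a score from 0 to 5. The primary Trial 2 outcome is binary (score 4 or 5, and retained). For that outcome, "Women who are not retained for 6-month follow-up will be counted as failures and will contribute to the analysis denominator". A secondary Wilcoxon rank-sum test then compares the full score between arms, with this limit: "This analysis will be restricted to women with an evaluable adherence composite score".

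Section 8.15.1, which covers both trials, adds: "Sensitivity analyses will exclude women who were not retained in care". It also sets the style of inference: "emphasis will be put on estimation and precision of measured effects, rather than null hypothesis testing".

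Three other places bear on the point.

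- Section 7.0 states the Trial 2 hypothesis that the strategy "will increase retention in care with functional PrEP adherence among HIV-negative pregnant women".
- Section 8.14.2 describes the design as "randomized 1:1 between the intervention and control arms (n=100 each), balanced (stratified) by site". The primary model adjusts for site; no such adjustment is stated for the Wilcoxon test.
- Section 8.14.1 describes the Trial 1 composite as calculated "with the approximately 10% of women lost to follow-up included in the denominator", and 8.14.2 uses the same 10% for Trial 2. Neither splits it by arm.

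The dichotomised medication possession endpoint in 8.15.4 also builds in retention and is analysed like the primary endpoints. The other uses of the score are binary (4-5, and 5 alone). The plan nowhere compares the full score in all randomised women.

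**The concern.** Being retained, and so having a score, happens after randomisation and is one half of what the intervention is hoped to change. If the intervention keeps in care women who take few doses, they pull down the intervention arm among those with a score. If it loses such women, that arm looks better. A comparison limited to retained women is then no longer protected by randomisation and may depart from the composite either way.

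What is at stake is interpretation. These pilots are meant to inform larger trials. A retained-only result called a sensitivity analysis will be read as a test of whether the composite holds up, although it answers a different question. The pilot would also lack a randomisation-based estimate on the full adherence scale. Two smaller points go with this: the score test leaves out the stratification factor, and it yields a p-value without an estimate, which sits poorly with the stated emphasis on estimation.

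**Working it through.** **Inputs from the plan.** Trial 2: 100 women per arm, composite 30% vs 50% (8.14.2, Table 4). Trial 1: 50 per arm, composite 75% vs 85% (Table 4). Loss about 10% overall. Two-sided 5% level.

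**Assumption.** Retention by arm, with r_C + r_I = 1.80 so that overall loss stays at 10%.

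**Step 1: the plan's own figures.** For the likelihood ratio chi-square test with n = 100 per arm and p̄ = 0.40, the noncentrality is 2n[KL(0.30, p̄) + KL(0.50, p̄)], where KL is the Kullback-Leibler divergence. On 1 df this gives 82.6% power, against 82% in the text and 83% in Table 4. The Wald interval width is 2 × 1.96 × √(0.50 × 0.50/100 + 0.30 × 0.70/100) = 26.6 points, against 26.7 in Table 4. Both reproduce.

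**Step 2: no composite difference (30% vs 30%, Trial 2).** The retained-only difference is p_I/r_I − p_C/r_C.

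- Control/intervention retention 92/88: 30/88 − 30/92 = 34.1% − 32.6% = +1.5 points.
- 90/90: 0.
- 95/85: 30/85 − 30/95 = 35.3% − 31.6% = +3.7 points.
- The mirror splits (88/92 and 85/95) give −1.5 and −3.7.

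**Step 3: the score test under the same null.** I simulated 40,000 trials per setting, with 50 women per arm in each of two sites. All retained women were taken as evaluable, and scores as uniform within 0-3 and within 4-5. The evaluable-only Wilcoxon test rejects in about 5% of trials at 92/88 and 7% at 95/85, against a nominal 5%.

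**Step 4: composite held at Table 4 values.**

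| Retention, control/intervention | Trial 2, composite difference 20 | Trial 1, composite difference 10 |
|---|---|---|
| 95/85 | 27.2 | 21.1 |
| 92/88 | 24.2 | 15.1 |
| 90/90 | 22.2 | 11.1 |
| 88/92 | 20.3 | 7.2 |
| 85/95 | 17.3 | 1.2 |

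For example, Trial 2 at 85/95 is 50/95 − 30/85 = 52.6% − 35.3% = 17.3. At 90/90 the excess over the composite comes only from the smaller denominator. Because the composite is fixed, adherence among retained women moves against retention by construction. The table therefore shows how far two estimands can separate. Trial 1 at 95/85 is the feasible limit, since it needs every retained intervention woman suppressed.

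**Step 5: power of the score comparison, 30% vs 50%.** Same simulation; in the all-randomised version, non-retained women rank below score 0.

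| Retention, control/intervention | Evaluable only | All randomised |
|---|---|---|
| 95/85 | 90% | 32% |
| 92/88 | 82% | 49% |
| 90/90 | 75% | 61% |
| 88/92 | 67% | 72% |
| 85/95 | 53% | 85% |

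At 90/90 the Mann-Whitney probability is 0.611 among evaluable women and 0.590 among all randomised. Stratifying the evaluable-only test by site changed power by 0.3 points or less, but no site effect was simulated.

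**The case against.** The strongest reply is that little depends on these analyses. They are secondary or sensitivity analyses in pilots sized on feasibility, no decision rule uses them, and the restriction is openly stated. The primary comparison already gives a randomisation-based answer at the 4-5 cut, apart from retained women whose data are missing. Section 8.15.4 tabulates retention and reasons for drop-out, though it does not say by arm, and promises detailed analysis plans. All of this stands, and it limits the weight of the point.

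The remedy can also be questioned. Placing a non-retained woman below a retained woman with no detectable drug is a value judgement. With equal composites, the all-randomised test rejects in about 6% of simulated trials at 92/88 and 14% at 95/85. Those rejections reflect a real retention difference and are not false positives, but they are not about drug level. That is why the comparison should be added and not substituted.

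A reader might infer more than the documents support:

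- *The ranges in step 4 measure bias.* They do not; they contrast two quantities that differ by definition.
- *Retention will differ by arm.* The plan gives no arm-specific figure, and its hypothesis concerns the composite, with no separate retention effect.
- *Intention to treat is breached.* Section 8.15.1 describes it as analysis by assigned arm, and the restricted analyses still do that.
- *The score test is seriously invalid.* If nobody's dosing changes and one arm retains ten more women per 100, all scoring 0 or 1, the evaluable-only test rejects in about 12-13% of trials. That needs every extra woman to be a very low scorer.

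**Conclusion.** The point holds as a minor one about two kinds of non-primary analysis. If retention differs by arm, the evaluable-only score test and the retained-only sensitivity analyses compare groups selected after randomisation and can differ from the composite in either direction. Neither can serve as a robustness check of the composite.

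The size is modest at the loss the plan expects. With no composite difference it is 1.5 to 3.7 points for retention gaps of 4 to 10 points, well inside an interval of about ±13 points, with score-test rejection of about 5% to 7%. These figures rest on the assumed retention splits and, for the score test, on the assumed score distribution and all retained women being evaluable. The primary analyses of both trials are unaffected. The omission of site and the lack of an effect estimate are read directly from 8.15.3 and need no assumption.

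**What to change.** In the SAPs still to be finalised:

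1. Stratify the Trial 2 score comparison by site (van Elteren test) and report the Mann-Whitney probability with a 95% CI.
2. Add, without replacing the evaluable-only comparison, the same analysis in all randomised women. Rank non-retained women below score 0, in line with the primary failure rule. Handle retained women without an assay result as in the primary analysis, and report their number by arm.
3. State that the evaluable-only and retained-only results describe adherence among retained women, are not robustness checks of the composite, and can differ from it in either direction. Show them beside retention by arm.

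The cost is wording and minor programming, with no new data. The downside lies in item 2: it mixes retention with drug level and partly repeats the primary analysis. It has less power than the evaluable-only test when retention is equal and much less when retention favours control (step 5). It gains power only when intervention retention is higher by about 3 points or more. Fixing these rules before arm-level data are seen avoids a post hoc choice.

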8.5 Recruitment and enrollment procedures

Staff will provide interested participants with additional information and referral to the study. Potential participants will be identified at any point in their pregnancy. All women attending the ANC clinic at enrolling study facilities who meet the eligibility criteria (section 8.3) will be invited to participate in the study. All participants will undergo an informed consent procedure to ensure they are well-informed about the study, its objectives, and its requirements (section 9.2)

8.5.1 Enrollment procedures for Trial 1

Following informed consent, HIV-positive pregnant women eligible for Trial 1 will be enrolled at the same visit. We will collect social, demographic, medical, and behavioral information from all participants. We will obtain from the locator information from the participant, including phone numbers, addresses, and directions. Participants will be randomly assigned to one of two study arms (control or intervention). Statistical software will be used to generate a list of random assignments with a 1:1 ratio, balanced for each site. The randomly generated numbers will be placed in opaque sealed envelopes and sequentially numbered with participant identification numbers.⁷³

8.5.2 Enrollment procedures for Trial 2

Following informed consent, HIV-negative pregnant women eligible for Trial 2 will first undergo screening for HIV and hepatitis B surface antigen (HBsAg). Specimens will be drawn; participants will be asked to return in 1-2 weeks to confirm their eligibility to initiate PrEP. During that return visit, candidates who remain eligible (i.e., do

not meet any exclusion criteria) will be formally enrolled at this visit. Similar to Trial 1, we will then collect social, demographic, medical, and behavioral information from all participants. We will obtain locator information from the participant, including phone numbers, addresses, and directions. Participants will be randomly assigned to one of two study arms (control or intervention). Statistical software will be used to generate a list of random assignments with a 1:1 ratio, balanced for each site. The randomly generated numbers will be placed in opaque sealed envelopes and sequentially numbered with participant identification numbers.⁷³

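### Randomisation is stratified by site and the primary models adjust for it, but the secondary PrEP-score test is unstratified and the mean-MPR comparison names no site adjustment

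*Combined protocol and SAP*

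**What the plan says.** Site is the stratification factor in both trials. Section 8.5 describes a "list of random assignments with a 1:1 ratio, balanced for each site". Section 8.14.1 has Trial 1 allocated "with randomization balanced (stratified) by site", and section 8.14.2 has Trial 2 "arms (n=100 each), balanced (stratified) by site".

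The primary analyses use the stratum. The linear-binomial models in 8.15.2 and 8.15.3 both carry site (country) as a covariate, and 8.15.2 gives control of site effects as the reason. Section 8.15.4 sends the dichotomised MPR endpoint (80% or more) through the same approach, so it is site-adjusted too.

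Two secondary comparisons differ:

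- **PrEP adherence score, 0 to 5 (8.15.3).** The plan states that "secondary analyses will compare the adherence composite scores between the study arms using a Wilcoxon rank-sum test". No stratification is named, and only women with an evaluable score are included.
- **Mean MPR, both trials (8.15.4).** The plan states that "the difference in means between study arms will be compared using a 95% CI". No model is named and site is not mentioned.

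Section 8.15.1 puts the emphasis on estimation and precision over hypothesis testing. Section 8.15.4 ends by promising detailed SAPs before each trial is analysed.

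**The concern.** Stratified 1:1 randomisation balances the arms within each site, so a difference between sites adds nothing to the sampling variance of the arm contrast. An analysis that ignores the stratum still counts that difference as noise. For a mean, the standard error is then overstated and the nominal 95% interval over-covers. For a rank test, the true size falls below 5% and power is lost.

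The plan is also uneven with itself: MPR is site-adjusted when dichotomised, but no adjustment is named for its mean, and no reason is given. In pilots of 50 and 100 women per arm that put precision first, this would be an avoidable loss. Open wording also leaves the choice between an adjusted and an unadjusted analysis to be made after the data are seen.

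**Working it through.** **The plan's own figures.** They cover only the binary primary endpoints. Section 8.14.1 says that "Power calculations were based on a two-sided likelihood ratio chi-square test for two proportions". Recomputing that test gives 24.1%, 51.6% and 82.8% for Trial 1 (Table 4: 24%, 52%, 83%) and 59.4%, 82.6% and 94.9% for Trial 2 (Table 4: 59%, 83%, 95%). The Table 4 interval widths also reproduce, using an n-1 variance. There is no stated power, SD or interval width for the score or for mean MPR, so what follows rests on assumptions.

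**Mean MPR.** Let σ be the within-site SD, d the site difference in units of σ, and w the share of women at one site. With n women per arm and stratified 1:1 allocation:

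- site-adjusted SE² = σ² × 2/n
- unadjusted SE² ≈ σ²[1 + w(1-w)d²] × 2/n
- ratio of widths = √[1 + w(1-w)d²]

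For equal sites (w = 0.5):

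| d | Calculation | Excess width |
|---|---|---|
| 0.2 | √(1 + 0.25 × 0.04) = 1.005 | 0.5% |
| 0.5 | √(1 + 0.25 × 0.25) = 1.031 | 3.1% |
| 0.75 | √(1 + 0.25 × 0.5625) = 1.068 | 6.8% |
| 1.0 | √(1 + 0.25 × 1) = 1.118 | 11.8% |

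A 30/70 split lowers this slightly: 0.4%, 2.6% and 10.0% at d = 0.2, 0.5 and 1.0.

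A simulation (20,000 runs per setting, 50 or 100 per arm, equal sites) agrees. Unadjusted coverage is about 95% at d = 0.2, 95.5-95.8% at 0.5 and 97.1-97.2% at 1.0; adjusted coverage stays at about 95%. Where the adjusted analysis has 80-81% power, the unadjusted one has about 80%, 79% and 73%.

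As an illustration, take a within-site SD of 20 MPR points (assumed). The full interval width in Trial 1 is 15.9 points adjusted, against 16.4 (d = 0.5) or 17.7 (d = 1.0) unadjusted. In Trial 2 it is 11.2 against 11.5 or 12.5.

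**PrEP score.** Inputs of the simulation:

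- 90 evaluable women per arm: 100 less the plan's 10% loss.
- 45 per arm per site: equal sites, assumed.
- Scores 0 to 5 with probabilities 0.25, 0.12, 0.15, 0.15, 0.18, 0.15 (assumed). The share scoring 4 or 5 is 0.33, in line with the plan's 30% control rate among 90% retained (0.30/0.90 = 0.33).
- Proportional-odds shifts for site and for treatment (treatment log odds ratio 0.75), 4,000 runs.

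| Share scoring 4-5, by site | Size: unstratified / stratified | Power: unstratified / stratified |
|---|---|---|
| 33% v 33% | 5.6% / 5.6% | 81% / 81% |
| 29% v 38% | 4.8% / 5.0% | 80% / 80% |
| 24% v 43% | 4.3% / 5.1% | 78% / 80% |
| 17% v 54% | 2.9% / 5.1% | 72% / 80% |

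The Monte Carlo standard error of a 5% size is √(0.05 × 0.95/4000) = 0.34 points. The drop to 2.9% is therefore clear, while the drop to 4.3% is modest.

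A second assumed score distribution, with the same numbers of women and runs, gave size 4.3% and power 75% v 77% at 21% v 40% between sites. At 14% v 49% it gave size 2.9% and power 64% v 70%. The absolute powers depend on the assumed treatment shift. The sizes agree, and the losses agree in scale: 2 points at a 19-point gap, and 6 to 8 points at 35 to 37.

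**The case against.** The case against giving this weight is strong on several counts.

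- **Silence is not a decision.** A reader might infer that mean MPR will be compared by a plain two-sample difference. Section 8.15.4 does not say so: it names no method and defers detail to later SAPs. The point stands only as something left unspecified. The Wilcoxon text is different, because there a specific unstratified test is named.
- **Not every comparison has an interval.** A reader might infer that both comparisons will carry intervals that are too wide. The planned Wilcoxon analysis reports no interval, so only conservative size and lost power can be claimed for it.
- **Dispensing practice.** A reader might expect the two countries to differ in dispensing. That fits Trial 1, where the local programme dispenses ART (8.6.1, 8.8.1). It does not fit Trial 2, where study staff dispense PrEP monthly at both sites (8.6.2, 8.8.2). Other site differences remain possible, but the documents give no size for any of them.
- **Small effect.** A reader might infer a material loss whenever the sites differ. Below about half a within-site SD it is negligible, and the larger Wilcoxon loss needs a gap of 35 points or more.
- **Low stakes.** These are secondary analyses in pilots sized on feasibility, and the error does not inflate false positives.

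All of this stands, and it sets the severity. It does not remove the point, because with equal sites the stratified analysis performs the same as the unstratified one. One further consideration favours stratifying: the score analysis is limited to evaluable women. If evaluability differs by arm and site, the within-site balance is disturbed, and leaving out site could then shift the comparison as well. The documents do not allow that to be sized.

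**Conclusion.** The point holds at low severity. The Wilcoxon test as written ignores the randomisation stratum, and the mean-MPR comparison does not say whether it uses it. If site predicts the outcome, the cost is a conservative test or an over-wide interval. For the score, size is about 4.3% with about 2 points of power lost at a 19-point site gap, and about 2.9% with 6 to 8 points lost at 35 to 37 points. For mean MPR, if it is left unadjusted, the excess width is about 3%, 7% or 12% at 0.5, 0.75 or 1.0 within-site SD, and under 1% at 0.2 SD.

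The site gaps, the MPR SD, the score distributions, the treatment shift and the equal site split are all assumptions. The direction of the effect does not depend on their exact values; the size depends on them entirely. The primary results are unaffected.

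**What to change.** In 8.15.3, replace the Wilcoxon rank-sum test with its site-stratified version (van Elteren), keeping the same evaluable population. In 8.15.4, and in the pending SAPs, state that the mean-MPR difference and its 95% CI come from a linear model with arm and site. A robust standard error is optional and does not follow from the argument about site. The wording should be settled before the data are analysed.

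The cost is SAP wording and one degree of freedom for site. Sample size, data collection and the primary analyses do not change.
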